#### F. SAE Reporting

SAEs that are unanticipated, serious, and possibly related to the study intervention will be reported to the Data Safety Monitoring Board, Penn State IRB, Penn State CTSI, and NIH in accordance with requirements.

- Unexpected fatal or life-threatening AEs related to the intervention will be reported to the NIH Program Officer within 7 days. Other serious and unexpected AEs related to the intervention will be reported to the NIH Program Official within 15 days.
- Anticipated or unrelated SAEs will be handled in a less urgent manner but will be reported to the Data Safety Monitoring Board, Penn State IRB, Penn State CTSI, NIH, and other oversight organizations in accordance with their requirements.
- In the AE summary of the Annual Data and Safety Monitoring Report, the Data Safety Monitoring Board will state that they have reviewed all AE reports.

#### G. Expectedness of SAEs

The Study PI and Independent Data Safety Monitoring Board will be responsible for determining whether an SAE is expected or unexpected. An event is considered expected if it appears on the List of Previously-Reported Medication Effects in Appendix C2. An adverse event will be considered unexpected if the nature, severity, or frequency of the event is not consistent with the risk information previously described for the intervention.

### V. Data Quality and Safety Review Plan and Monitoring

#### A. Data Quality and Management

- 1) Description of Plan for Data Quality and Management— The PI or study staff will review all data collection forms on an ongoing basis for data completeness and accuracy as well as protocol compliance. All data for this project will be promptly entered into a computerized database. Subjects will enter data directly into REDCap when completing self-administered questionnaires in REDCap. Research staff will enter data from paper forms into REDCap. Data can also be directly entered into REDCap. Subject identifications will be kept separate in locked files and will be destroyed when no longer needed for the project. To minimize errors, measures will be verified prior to data entry and computer verification will be employed during data entry. Data files will be backed up and archived regularly.
- 2) Frequency of Data Review for this Study— The frequency of data review for this study is summarized in the following Table:

Data type	Frequency of review	Reviewer
Subject accrual (including accrual of minority subjects)	Every 6 months	PI, Data Safety Monitoring Board
Status of all enrolled subjects, as of date of reporting	Every 6 months	PI, Data Safety Monitoring Board
Adherence data regarding study visits and intervention	Every 6 months	PI, Data Safety Monitoring Board
Adverse Events (including out-of-range patient-reported safety assessments)	Every 6 months	PI, Data Safety Monitoring Board
SAEs	Per occurrence	PI, Data Safety Monitoring Board, NIH, IRB, CRC/CTSI

## B. Subject Accrual and Compliance

- 1) Measurement and Reporting of Subject Accrual, Compliance with Inclusion/Exclusion Criteria—Review of the rate of subject accrual and compliance with inclusion/exclusion criteria (verifying that all randomized subjects meet the inclusion/exclusion criteria) will occur every 6 months to ensure that a sufficient number of participants are being enrolled and that they meet eligibility criteria and the targeted ethnic diversity goals outlined in the grant proposal (Targeted/Planned Enrollment Table). If recruitment goals are not being met, recruitment efforts will be targeted to meet any unmet goals. To report data on enrollment and subject demographics, we will use Tables 1 and 2 in Appendix A.
- 2) Measurement and Reporting of Participant Adherence to Treatment Protocol

Data on adherence to the treatment protocol will be collected weekly by research staff and reviewed every 6 months by the PI, the study statistician, and the Data Safety Monitoring Board. Adherence of participants will be evaluated by recording attendance at each class. Previous MBSR studies report adherence rates varying from 70-85%. If adherence falls below 75%, which might inhibit the ability of the study to test its primary hypotheses, the PI will suggest a conference call for study investigators to discuss methods for improving adherence.

## C. Justification of Sample Size

The goal of this study is to compare the effectiveness of a six-month MBSR intervention versus SME control intervention in improving glucose control and other important outcomes in patients with uncontrolled diabetes. The primary outcome is hemoglobin A1c, which is a measure of average glucose control over the past 3 months. A sample size of 290 subjects (145/group) will provide 80% power to detect a clinically significant 0.5% absolute difference in the mean change in A1c from baseline to month 6, assuming a standard deviation of 0.9%, between the two groups using a two-sided test having a significance level of 0.05. The sample size estimate was based on the intent-to-treat principle and inflated to account for the potential of 15% subject dropout.

## D. Stopping Rules

This study will be stopped prior to its completion if: (1) the intervention is associated with adverse effects that call into question the safety of the intervention; (2) difficulty in study recruitment or retention will significantly impact the ability to evaluate the study endpoints; (3) any new information becomes available during the trial that necessitates stopping the trial; or (4) other situations occur that might warrant stopping the trial.

The PI will include an assessment of futility in the annual progress report to NIH and will consult with the study monitors and the NIH Program Official to assess the impact of significant data loss due to problems in recruitment, retention, or data collection.

## E. Designation of a Monitoring Committee

The Data Safety Monitoring Board for this study will perform the monitoring outlined in this Data and Safety Monitoring Plan. The independent Data Safety Monitoring Board is well qualified for this role as it is led by a family physician and experienced diabetes researcher, and includes a licensed clinical psychologist and an experienced DSMB statistician. None of the Data Safety Monitoring Board members are involved in this grant as key personnel. Therefore, the Data Safety Monitoring Board will be able to carry out this Data and Safety Monitoring Plan independent of the PI and research team.

## **F. Safety Review Plan**

Study accrual, subject retention, subject adherence to intervention sessions, and study safety will be reviewed by the DSMB every 6 months (and more frequently if needed) starting 6 months after randomization of the first study cohort. Progress reports, including patient recruitment, retention/attrition, and AEs will be provided to the Data Safety Monitoring Board following each of the reviews. An Annual Report will be compiled and will include a list and summary of AEs. In addition, the Annual Report will address (1) whether AE rates are consistent with pre-study assumptions; (2) reason for dropouts from the study (only blinded information; unblinded information from the open-ended attrition item will not be provided); (3) whether all participants met entry criteria; (4) whether continuation of the study is justified on the basis that additional data are needed to accomplish the stated aims of the study; and (5) conditions whereby the study might be terminated prematurely. The Annual Report will be sent to the Data Safety Monitoring Board and will be forwarded to the IRB, NIH, and other applicable recipients who will review the progress of this study on an annual basis.

## **G. Study Report Outline for the Data Safety Monitoring Board (Interim or Annual Reports)**

The study team will generate Study Reports for the Data Safety Monitoring Board, and will provide information on the following study parameters: recruitment, enrollment, retention, demographics, subject status, adherence to study intervention, patient-reported safety assessments and AE data. Study Reports for the Data Safety Monitoring Board will not include data on primary or secondary endpoints as there are no interim analyses planned for the study, with the exception of safety outcomes.

Study Report tables will be generated only from aggregate (not by group assignment) baseline and aggregate safety data for the study population. We will use the Study Report Outline in Appendix B.

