Randomization to MBSR or SME control will be performed within REDCap using a pseudo-random number generator via the PLAN procedure within SAS software, version 9.4 (SAS Institute Inc., Cary, NC). Personnel in the Department of Public Health Sciences will use the PLAN procedure within SAS software to generate a randomization list using variable-size, random permuted blocks to ensure that the number of subjects in each treatment arm is balanced after each set of B randomized subjects, where B is the block size. Using a 1:1 allocation ratio, there will be 145 subjects assigned to each study group. Randomization will be stratified by insulin vs. non-insulin treated subjects to make sure the two groups are balanced as this is a potential confounder. Personnel in the Department of Public Health Sciences will choose the block sizes without revealing it to any of the blinded investigators or study personnel who will be collecting and reviewing outcomes data. Study group data will be presented in a blinded fashion within DSMB reports.

Randomization to MBSR or SME control will be performed by the SME instructors in REDCap during the Randomization phone call as described below. Study group assignments will not be communicated to research personnel who will be collecting and reviewing outcomes data. The SME instructors will communicate the study group assignments to the subjects and the MBSR instructors. The subjects and instructors will be asked to keep the assignments concealed from the blinded investigators and study personnel. The PI, research coordinators and all study personnel involved in the collection and review of outcomes data will be blinded.

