### **C. Confidentiality During Adverse Event (AE) Reporting**

AE reports and annual summaries will not include subject or group-identifiable material unless requested by the DSMB due to safety concerns. Each report will only include the identification code.

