### C. AE Attribution Scale (Relatedness)

To assess the relationship of an event to the study intervention, the following guidelines are used:

1. Related (Possible, Probable, Definite)
  - a. The event is known to occur with the study intervention.
  - b. There is a temporal relationship between the intervention and event onset.
  - c. The event abates when the intervention is discontinued.
  - d. The event reappears upon a re-challenge with the intervention.
2. Not Related (Unlikely, Not Related)
  - a. There is no temporal relationship between the intervention and event onset.
  - b. An alternate etiology has been established.

AEs will be categorized according to the likelihood that they are related to the study intervention. Specifically, they will be labeled as "0 = Not related, 1 = Unlikely related, 2 = Possibly related, 3 = Probably related, or 4 = Definitely related. Additionally, we will use [name] of Previously-Reported Meditation Effects (See Appendix C2) to determine whether the symptom is an expected effect, and to determine the symptom Domain out of 8 domains including a Diabetes Domain (See Appendix D) in addition to [name] 7 domains (Affective, Cognitive, Conative, Perceptual, Sense of Self, Social, and Somatic).

Relatedness to treatment will be assessed according to 8 causality and relatedness criteria that regulatory agencies such as the World Health Organization (WHO), the Federal Drug Administration (FDA), and the National Institutes of Health (NIH) use to make health policy decisions (NIH, 2016; Agbabiaka et al., 2008; Turner, 1984; WHO, 2016). These criteria are designed to assess treatment-relatedness in individual cases in the absence of prospective or epidemiological (base rate) data. The 8 standard causality/relatedness criteria are 1) prior published reports, and expert judgment, 2) subjective attribution, 3) temporal proximity (challenge), or exacerbation, 4) consistency, 5) dose-response gradient 6) de-challenge, 7) re-challenge, 8) specificity, (Turner, 1984; Naranjo, 1986; Naranjo, 1982; Naranjo, 1981; Hill, 1965; Hill, 2015; Gallagher et al., 2011; Theophile et al., 2010).

The Relatedness Criteria Definitions table below provides detailed definitions for assessing relatedness in individual cases.

Relatedness Criteria Definitions Table	

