- e) Description of SAE (CTCAE term) (The research coordinator will enter a symptom, condition/diagnosis (if available), or procedure as the primary event. If a condition/diagnosis has not been identified, the symptom (e.g., chest pain) will be entered, and the event will be updated to the condition/diagnosis when available [e.g., Cardiac Arrest]).
- f) Unexpectedness (1 = Yes, 2 = No) (Refer to List of Previously-Reported Meditation Effects in Appendix C2 and Diabetes Domain Expected Events in Appendix D).
- g) Age of subject (at time of onset)
- h) Sex of subject
- i) Brief description of the nature of the SAE (with no personal identifiers)
- j) Category of SAE (Death with date of death, Life threatening, Hospitalization-initial or prolonged with admission date and discharge date, Disability/incapacity, Congenital anomaly/birth defect, Required intervention to prevent permanent impairment, or Other: \_\_\_\_\_)
- k) Relatedness (using the Relatedness Criteria Definitions Table above in section IV-C and the List of Previously-Reported Meditation Effects in Appendix C2). (Unrelated [clearly not related to the intervention], Possible [may be related to intervention], Definite [clearly related to intervention]).
- l) Whether study intervention was discontinued due to the event? (Yes or No or N/A – event occurred prior to start of study intervention)
- m) What medications or other steps were taken to treat the SAE? \_\_\_\_\_
- n) Intervention type (Medication or nutritional supplement, Device, Surgery, Behavioral/lifestyle)
- o) List any relevant tests, laboratory data, and history, including preexisting medical conditions: \_\_\_\_\_
- p) Is this the final report? (Yes or No)

E.1 Adverse events will be assessed according to the measures and schedule described in the table below.

Name of measure	Visit # 1 Baseline	Visit #2 Follow-up Phone Call after Class #4 (Middle of 8-wk MBSR/SME)	Visit #3 2-month (End of 8-wk MBSR/SME)	Visit #4 6-month (After Booster session #4/End of Study)
PHQ-9	x		x	x
Stress Experience Survey*	x	x	x	x
Subject initiated (passive monitoring)	Ongoing			
Dropout-reason form	Ongoing, as dropouts occur			
*The Stress Experience Survey, includes questions about the most common meditation-related symptoms and other stress related symptoms. These questions may result in the participant reporting an AE. If this occurs, the AE will be marked as "expected" and compared to Baseline and previous visit responses for proper documentation.				

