### E.3 Other Measures for Monitoring AEs

**E.3.1 Stress Experience Survey [Adapted from [name] program-specific adverse effects (MBP-SPEC-AE) survey].** CONSORT-Harms guidelines (Ioannidis et al., 2004) recommend using standardized and validated scales that assess treatment-specific symptoms, because they have more accurate detection rates than passive monitoring (Stephens et al., 1998) or open-ended queries (Wallin and Sjovall, 1981; Bent et al., 2006) and are low cost, low burden and require no special training to administer.

To accommodate these recommendations, and to create a systematic query of treatment-specific symptoms in all treatment arms, the research coordinator will administer the Stress Experience Survey to specifically query the most common meditation-related side effects (anxiety, depression, dissociation, re-experiencing of traumatic memories etc.) found in 8-week MBIs using patient-reported outcomes measurement information system (PROMIS) or NeuroQol items (or other validated scales if construct is not available). The Stress Experience Survey includes questions about the most common meditation-related symptoms (items 1 to 10), as well a question about other stress-related symptoms. This survey was adapted from [name] MBP-Specific Adverse Effects Survey (Britton\_Version9.18.19), which represents the 10 most common meditation-related symptoms from the Varieties of Contemplative Experience Phenomenology Codebook (Lindahl et al., 2017), as replicated in an NIH-funded mindfulness-based intervention clinical trial (Britton, in prep). Subsequently, the research coordinator will record any item occurring more frequently compared to baseline, or previous visit responses, as an Adverse Event and assess its severity (using the Severity Grading Tool in Appendix C1) and relatedness (using the Relatedness Criteria Definitions Table above in section IV-C). Subjects will be asked to provide further detail (i.e., date of onset, symptomology, circumstance surrounding the event, relatedness to the intervention, etc.) on any AE/SAE reported in the Stress Experience Survey. These details will be used to assess the need for treatment modification, referrals and reporting.

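### Routine DSMB tables are not split by arm, so the board does not routinely see the randomized comparison of common non-serious adverse events; a closed masked-arm report would supply it cheaply

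*Combined protocol and SAP*

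**What the plan says.** **Board reports.** DSMP V.G, and Appendix B in the same words: "Study Report tables will be generated only from aggregate (not by group assignment) baseline and aggregate safety data for the study population". V.G has the study team generate the reports. It keeps primary and secondary endpoints out of them because no interim analyses are planned, but makes an exception for safety outcomes. In Appendix A, Tables 3 to 7 are listings by participant; Tables 6 and 7 give event terms, relatedness, expectedness and action. None has an arm column.

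**Other wording on group data.** Protocol 7.2.4: "Study group data will be presented in a blinded fashion within DSMB reports". DSMP III.C says that adverse event (AE) reports and annual summaries "will not include subject or group-identifiable material unless requested by the DSMB due to safety concerns".

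**Review.** The board reviews safety every six months (V.F) and serious adverse events (SAEs) as they occur (V.A). The annual report compares AE rates with pre-study assumptions (V.F).

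**Stopping.** The first ground, in protocol 9.8 and DSMP V.D, is that "the intervention is associated with adverse effects that call into question the safety of the intervention". No threshold is given, and section 9.7 marks statistical tests as not applicable.

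**Symptom survey.** DSMP IV.E.3.1 gives the Stress Experience Survey "to create a systematic query of treatment-specific symptoms in all treatment arms", and the coordinator "will record any item occurring more frequently compared to baseline, or previous visit responses, as an Adverse Event". A footnote in E.1 has AEs that arise from the survey marked as expected and "compared to Baseline and previous visit responses for proper documentation".

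**Relatedness.** The criteria in IV.C are meant for individual cases "in the absence of prospective or epidemiological (base rate) data".

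**The concern.** DSMP IV.D names depression, anxiety, dissociation and re-experiencing of trauma as risks of meditation. Both arms are asked about such symptoms at baseline and three times after randomization. Under the recording rule, any item that becomes more frequent is an AE in either arm, so background events may be numerous, and the expected label makes each one unremarkable by itself.

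The relatedness criteria work case by case and assume that no base rate is available. Here one is: the SME arm answers the same survey at the same times. When the arms are not shown separately, an excess in one arm and an even background can give the same listing.

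The right to request group data needs a safety concern to arise first, from single cases or from tables that cannot show an imbalance. The annual comparison with pre-study assumptions helps little, because the only range given for non-serious events with some impairment is 1-25% (IV.D).

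**Working it through.** **1. Passages side by side.**
- V.G and Appendix B: routine tables, not by arm, no exception mentioned.
- III.C: AE reports and annual summaries, no group-identifiable content unless the board asks. This can stand beside V.G as an exception to a routine rule, but neither section refers to the other, and III.C does not say who would meet a request.
- Protocol 7.2.4: the blinded presentation of study group data can mean arms under masked labels, which does not fit V.G, or no arm split at all, which does.

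These are gaps in alignment, not outright contradictions.

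**2. What pooling hides.** The plan gives no figure to reproduce here, so the event counts below are assumed. From the plan: 145 per arm (7.2.4).
- 22 vs 7, 18 vs 11 and 15 vs 14 each give 29/290 = 10.0%.
- 22 vs 7: 22/145 = 15.2%, 7/145 = 4.8%, difference 10.3 points; Wald 95% CI 3.5 to 17.1; Fisher p = 0.005; pooled z = 2.94.
- 18 vs 11: difference 4.8 points; 95% CI -2.1 to 11.7; Fisher p = 0.24.

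**3. Allowing for classes.** Section 8.2 plans classes of 18 and an ICC of 0.08 for HbA1c, with a design effect of 2.36. That figure is reproduced by 1 + (18 - 1) × 0.08 = 2.36. No ICC is given for AEs, so I assume 0.02 to 0.08 and divide z by the square root of the design effect.

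| Assumed ICC | Design effect | z, 22 vs 7 | p |
|---|---|---|---|
| 0.02 | 1.34 | 2.54 | 0.011 |
| 0.05 | 1.85 | 2.16 | 0.031 |
| 0.08 | 2.36 | 1.91 | 0.056 |

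For 18 vs 11 the clustered p is 0.237 to 0.372.

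**4. When it would show.** Randomization milestones are from section 4.2.3, halved for each arm, with assumed event rates close to 22 vs 7.

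| Randomized | Assumed split | p at ICC 0.02 / 0.05 / 0.08 |
|---|---|---|
| 72 | 5 vs 2 of 36 | 0.303 / 0.380 / 0.437 |
| 120 | 9 vs 3 of 60 | 0.115 / 0.179 / 0.235 |
| 174 | 13 vs 4 of 87 | 0.047 / 0.091 / 0.135 |
| 230 | 17 vs 6 of 115 | 0.037 / 0.075 / 0.116 |

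These treat everyone randomized as fully observed. Survey events arise at the call after Class #4, at 2 months and at 6 months, so the real dates are later. If six-month follow-up is needed, the result for 174 (planned for month 48) comes nearer month 54.

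**5. Rare serious events.** IV.D puts serious effects below 1%. A split of 2 vs 0 of 145 gives Fisher p = 0.50.

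**6. Multiplicity.** The survey has 10 symptom items. If they were independent and each tested at 0.05, the chance of at least one false signal per look would be 1 - 0.95^10 = 0.40.

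**The case against.** The strongest reply is that pooling is a deliberate choice with a way out. It is stated twice in the same words. It suits a design in which the blinded team may not know even the arm sizes within a cohort. The board includes an experienced statistician, can meet more often than every six months, and can ask for group data. Part of this stands: there is a working safeguard. It does not settle the matter. Protocol 7.2.4 itself foresees study group data in board reports, V.G excepts safety outcomes from its ban on interim data, and a closed report leaves the investigator and coordinators blinded.

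Four further points stand in full.
- The listings hold more than pooled rates. Relatedness is rated by staff blinded to arm, but partly from participants who know theirs and on criteria specific to meditation, so it carries some information about arm.
- For the same reason, relatedness detail in an A/B table could reveal which arm is MBSR.
- PHQ-9, GAD-7 and the Hypoglycemia Survey also stand under outcome headings in protocol Table 3, so it would be too strong to say that a report by arm shows no outcome data.
- The benefit is shown only with assumed counts and is modest for most of the trial.

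A reader might infer that the board can never see the arms. DSMP III.C says otherwise. A reader might also infer that the first stopping ground cannot be applied without a comparison by arm. Neither 9.8 nor V.D requires one or says who applies the rule.

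**Conclusion.** The point holds as a gap in routine monitoring. The board lacks, by default, the comparison most informative about common non-serious events, although it has case-level information and a right to ask. The documents do not support reading this as a failure of oversight or as a flat contradiction between sections.

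The size is moderate. On the assumed counts, pooling can conceal a 10-point difference that a table by arm would display. That difference stands out from chance only late in accrual and depends on the ICC. A 5-point difference would remain unresolved even at full size. For rare serious events, review of each case is more informative than an arm table. A board need not wait for p < 0.05: a growing imbalance would give it an informed reason to use its right under III.C. The conclusion that the arms are not routinely shown rests on the text and the table shells alone; the figures rest on assumed counts and an assumed AE ICC. This is a worthwhile, inexpensive improvement and not a condition for the trial's validity.

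**What to change.** 1. **DSMP V.G and Appendix B.** Keep the open report pooled. Add a closed six-monthly report, for the board only and under the existing exception for safety outcomes, with counts by masked arm (A/B) of AEs, SAEs, withdrawals and the out-of-range flags already in Appendix A, Table 5. Leave meditation-specific relatedness detail out of these tables. Decode on the board's request.
2. **Preparer.** Name someone who already holds assignments, such as the Public Health Sciences randomization staff or the data manager (7.2.4). State the firewall from the study team and from the study biostatistician, who may not analyse arm-identifying data before unblinding (7.2.3). The accelerometer text in 7.2.3 writes data manager and statistician as one item, so say whether these are separate people. If they are not, the randomization staff remain, and the plan must give them access to the AE data.
3. **Alignment.** In 7.2.4, say that group data appear by masked arm in the closed report only. In III.C, say whether A/B tables count as group-identifiable and who meets a request. Cross-refer V.G and Appendix B to III.C.
4. **Limits to state.** The comparison is descriptive, without efficacy testing. PHQ-9, GAD-7 and hypoglycemia appear by arm only as threshold safety flags. Note clustering, multiplicity over symptoms and looks, and low power until late accrual.

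The cost is DSMP wording, a named preparer, a firewall and a little extra reporting work. The trade-off is that some measures also listed as outcomes reach the board by arm in thresholded form.
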